#### **8.4.6 Guidelines for Dose Adjustments**

Dose adjustments will be guided by Hb concentrations and the Guidelines for Dose Adjustment (see below). Hb will be monitored via central laboratory throughout the study to determine if the dose of study drug (vadadustat or epoetin alfa) will be adjusted, interrupted, or maintained as follows:

- Dose adjustments are based on the investigator's clinical discretion, incorporating the protocol guidance below as well as the subject's current Hb level, trajectory, and variability; symptoms; cardiovascular risk; and other features of his/her clinical condition(s).
- If a dose increase or decrease is required to achieve and maintain Hb levels within the target range of 10.0 to 11.0 g/dL, inclusive, dose is adjusted by 1 dose level (for vadadustat 1 tablet [150 mg], for epoetin alfa approximately 25%).
- In general, do not increase the dose more frequently than once every 4 weeks. A one-time dose increase after 2 weeks is allowed on only two occasions.
  - A subject's dose may be increased by 1 dose level if the subject has a decline in Hb  $\geq 0.5$  g/dL from Baseline/Day 1 in the first 2-week period (the initial period from Baseline/Day 1 to Week 2 following conversion from prior epoetin alfa therapy).
  - A subject's dose may also be increased by 1 dose level in the first 2-week period after initiation of TIW dosing (from Week 12 to Week 14) for subjects that meet criteria for transitioning from daily to TIW dosing.

- Reduce or interrupt the dose in the setting of a rapid rise in Hb (defined as >1.0 g/dL in any 2-week period)
- Reduce or interrupt the dose in the setting of Hb >11.0 g/dL
- Interrupt the dose in the setting of a Hb >12.0 g/dL until Hb value falls below 11.0 g/dL. After Hb falls below 11.0 g/dL, restart study drug and consider restarting at a lower dose.

**Note:** The minimum dose of vadadustat will be 150 mg daily or TIW (1 tablet daily/TIW) and the maximum dose will be 900 mg daily or TIW (6 tablets daily/TIW).

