## 5.5 Safety Endpoints

Safety endpoints in this study include the following:

- AEs
- Vital sign measurements and clinical laboratory values
- Hb >12.0 g/dL, >13.0 g/dL, or >14.0 g/dL
- Hb <8.0 g/dL and decline in Hb  $\geq$ 0.5 g/dL from Baseline Hb (Main Study);  
Hb <7.5 g/dL and decline in Hb  $\geq$ 0.5 g/dL from Baseline Hb (ESA hyporesponder parallel study)
- Hb increase >1.0 g/dL within any 2-week interval

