### **7.6.2 Temporary Interruption of Study Drug**

Subjects who temporarily interrupt their study drug (vadadustat or epoetin alfa) after receiving the first dose and prior to completion of the study, will continue with the study visits, safety assessments, and other activities as deemed applicable through Week 20, and will complete the 4-week Safety Follow-Up Period and the Visit 15/Week 24 assessments (see [Appendix A](#): Schedule of Activities).

During the study, a subject may interrupt study drug (vadadustat or epoetin alfa) for any of the following reasons:

- AE
- Missed dialysis visit (epoetin alfa arm)
- Investigator's discretion
- Rapid rise in Hb (defined as >1.0 g/dL in any 2-week period)
- Hb above 11.0 g/dL
- ESA use (vadadustat arm)

Unless contraindicated, treatment will be resumed whenever possible and assessed at every visit following study drug interruption.

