##### **8.4.9.1 RBC Transfusion**

Investigators will use their local institution's transfusion guidelines when determining whether to transfuse a study subject. In general, in the event of an acute or severe loss of blood, a RBC transfusion will be administered as clinically indicated. In less severe instances but where there may be worsening of anemia or moderate to severe symptoms of anemia, RBC transfusions are permitted at the discretion of the investigator given medical necessity. Study drug (vadadustat or epoetin alfa) may be continued during the transfusion period.

Reasons for RBC transfusion will be captured in the appropriate CRF.

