##### **8.4.9.2 ESA Use**

ESA administration will be allowed when medically necessary at the discretion of the investigator. In general, ESA will not be administered in subjects with Hb  $\geq 8.5$  g/dL, and ESA will be stopped when Hb  $\geq 9.0$  g/dL. ESA therapy will be administered using an approved ESA and dosing as per the local institution's guidelines and per the approved product label.

While receiving ESA therapy, subjects randomized to vadadustat must temporarily interrupt vadadustat. A minimum interval will be observed prior to restarting vadadustat after the last dose of ESA, and treatment will be resumed after the following intervals:

- 2 days after last dose of epoetin alfa
- 7 days after last dose of darbepoetin alfa
- 14 days after last dose of methoxy polyethylene glycol-epoetin beta

Following ESA administration, vadadustat will be resumed at the same dose as previously used or with one additional tablet (+150 mg) at the discretion of the investigator.

Reasons for ESA use will be captured in the appropriate CRF.

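### The rapid-rise dosing rule (8.4.6) and the resumption rule after ESA rescue (8.4.9.2) can conflict when vadadustat is restarted, and the rapid-rise safety endpoint does not separate rises that follow rescue

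*Protocol*

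**What the plan says.** **Dose adjustment.** Protocol section 8.4.6 lists this among its guidelines: "Reduce or interrupt the dose in the setting of a rapid rise in Hb (defined as >1.0 g/dL in any 2-week period". The rule has no exception for a rise that follows rescue, and the Dosage and Regimens row of the synopsis repeats it. The section opens with a qualifier: "Dose adjustments are based on the investigator's clinical discretion, incorporating the protocol guidance below as well as the subject's current Hb level, trajectory, and variability". Section 7.6.2 is permissive too: "During the study, a subject may interrupt study drug (vadadustat or epoetin alfa) for any of the following reasons", and rapid rise is one of the reasons listed.

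**ESA rescue.** Section 8.4.9.2 states: "While receiving ESA therapy, subjects randomized to vadadustat must temporarily interrupt vadadustat". It sets minimum gaps before restart of 2 days after epoetin alfa, 7 after darbepoetin alfa and 14 after methoxy polyethylene glycol-epoetin beta. On the restart dose it says: "Following ESA administration, vadadustat will be resumed at the same dose as previously used or with one additional tablet (+150 mg". The choice between those two is left to the investigator. In general, ESA is not given at Hb 8.5 g/dL or above and is stopped at 9.0 or above. The Rescue Therapy Guidelines row of the synopsis repeats this.

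**Transfusion.** Section 8.4.9.1 says: "Study drug (vadadustat or epoetin alfa) may be continued during the transfusion period". It sets no dose.

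**Endpoint.** Section 5.5 lists "Hb increase >1.0 g/dL within any 2-week interval" as a safety endpoint, without qualification. Section 11.7 tabulates all Hb-related safety endpoints by treatment group, descriptively.

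**The concern.** A subject rescued with ESA can have a hemoglobin rise that meets the 8.4.6 definition because the rescue worked. At restart, one section then points to a reduced or withheld dose, while the other offers only the previous dose or a higher one. Nothing says which prevails, so the post-rescue dose may depend on which section a site consults. That dose feeds into later Hb, including the Weeks 10 to 12 average behind the primary endpoint. Section 13.2 makes an incorrect dose a deviation that must be notified to the sponsor, so a site that follows either section could be questioned under the other.

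The endpoint has a related weakness. Safety against epoetin alfa is part of the primary objective (5.1), and section 6.3 names rapid Hb rise as the risk to be mitigated at 750 and 900 mg. A rise produced by rescue ESA or donor blood counts the same as one produced by study drug. The arm with more rescue will therefore tend to show more rapid-rise events, whatever the study drug does.

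**Working it through.** The protocol gives no figure to reproduce here: section 11.1 states no power, effect size or SD. The check compares the passages and then asks whether the protocol's own thresholds can bring them into conflict.

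**Step 1. Where the rules overlap.**

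| Situation | 8.4.6 if Hb rose >1.0 g/dL in 2 weeks | Rescue section | Compatible? |
|---|---|---|---|
| Vadadustat arm, during ESA rescue | Reduce or interrupt | Interrupt (8.4.9.2) | Yes |
| Vadadustat arm, at restart after ESA rescue | Reduce or interrupt | Same dose or +150 mg (8.4.9.2) | No |
| Either arm, around a transfusion | Reduce or interrupt | May be continued (8.4.9.1) | In tension only |

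The direct conflict is confined to the second row.

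**Step 2. Can ESA rescue produce the trigger?** Inputs: rescue generally starts below 8.5 g/dL and stops at 9.0 or above (8.4.9.2); the trigger is a rise strictly above 1.0 (8.4.6). Rise = Hb at stop minus Hb at start. The stop values above 9.0 are assumptions, since the protocol gives no rate of rise under rescue.

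| Hb at start | Stop at 9.0 | Stop at 9.3 (assumed) | Stop at 9.5 (assumed) |
|---|---|---|---|
| 7.5 | 1.5, trigger | 1.8, trigger | 2.0, trigger |
| 7.9 | 1.1, trigger | 1.4, trigger | 1.6, trigger |
| 8.0 | 1.0, no | 1.3, trigger | 1.5, trigger |
| 8.2 | 0.8, no | 1.1, trigger | 1.3, trigger |
| 8.4 | 0.6, no | 0.9, no | 1.1, trigger |

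A stop at exactly 9.0 triggers the rule only for starts below 8.0. The protocol anticipates such values: section 5.5 includes Hb below 8.0 (Main study) and below 7.5 (hyporesponder study) in its low-Hb safety endpoints.

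**Step 3. Timing.** The rise must also fall within 2 weeks. Restart 2 or 7 days after the last ESA dose lies inside that window; a 14-day gap uses all of it. Conflict is therefore possible but not certain, and a slow rescue would not trigger the rule.

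**Step 4. How many subjects?** The protocol states no expected rescue rate. The nearest figure is withdrawal for worsening anemia in the earlier hemodialysis study (section 4.2): 0 of 30 on 300 mg daily, 1 of 33 on 450 mg daily and 6 of 31 on 450 mg TIW. The Main study plans 15 + 15 vadadustat subjects in the low-dose stratum and 15 + 15 + 15 in the high-dose stratum, 75 in all (study schematic).

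- Daily cohorts: 75 x 0/30 = 0; 75 x 1/33 = 2.3. About 0-2 subjects.
- TIW cohort: 6/31 = 19%, usable only as an upper bound on this proxy.

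These are proxies for subjects rescued. Only some rescues would also meet the more-than-1.0-in-2-weeks condition.

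**The case against.** The best defense is that the text already contains the answer. Section 8.4.6 is guidance under clinical discretion that expressly takes account of trajectory, and 7.6.2 says only that drug may be interrupted. Vadadustat is already on hold during ESA rescue, so the instruction to reduce or interrupt has been met while Hb is rising. Section 8.4.9.2 then deals specifically with restart, and a specific rule would normally be read as overriding a general one.

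Much of this stands, and it narrows the point to restart. It does not remove it. The discretion in 8.4.9.2 covers only the same dose or a higher one, the protocol nowhere says that the specific rule prevails, and section 6.3 calls the dose-adjustment algorithm strict and relies on it to limit rapid rises.

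On the endpoint, counting every rise whatever its cause is a legitimate safety summary. ESA rescue and transfusion are separate endpoints (5.3.2.1), data are listed by subject, and the SAP, which is not shown, may flag post-rescue values. That supports keeping the all-values count. The protocol itself nevertheless fixes the unqualified definition, although it takes rescue into account in the TIW transition criteria (8.4.5.2) and the per-protocol population (11.2).

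A reader might infer more than the documents support:

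- **Two binding, opposite orders.** The discretion wording rules this out, and for transfusion 8.4.9.1 is merely permissive.
- **Rescue scored as study-drug harm.** No passage attributes these events to study drug; the table is descriptive.
- **A large number of cases, by applying 19% to the 75 subjects.** That is a withdrawal rate, not a rescue rate, from a cohort that started on TIW dosing. Main-study subjects start on daily dosing.
- **The same distortion for Hb above 12.0 g/dL.** ESA rescue generally stops at 9.0, and no route from there to 12.0 is shown.

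**Conclusion.** The point holds in a narrow form. Sections 8.4.6 and 8.4.9.2 give incompatible directions when vadadustat is restarted after ESA rescue and Hb has risen by more than 1.0 g/dL within 2 weeks. The protocol's thresholds permit this, clearly so for rescues begun below 8.0 g/dL, but do not make it universal. Discretion softens the conflict without settling precedence. The transfusion text is a lesser tension.

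Separately, the 5.5 endpoint as tabulated under 11.7 mixes rises that follow rescue with rises on study drug alone, which blurs the by-arm safety comparison.

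The size cannot be derived from the protocol. About 0-2 of 75 Main-study vadadustat subjects rests on treating withdrawal for worsening anemia in two small daily-dosing cohorts as a stand-in for rescue. Subjects can be rescued without withdrawing, so the proxy may be low; not every rescue meets the trigger, so it may also be high. There is no proxy for the 15 vadadustat subjects planned in the hyporesponder study. The case for change rests on clarity and low cost rather than on a large expected count.

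**What to change.** 1. Reconcile 8.4.6 with 8.4.9.1 and 8.4.9.2, and the matching synopsis rows (Dosage and Regimens; Rescue Therapy Guidelines), by stating which passage governs when a rise above 1.0 g/dL in 2 weeks follows ESA rescue or transfusion. Which rule prevails is a clinical decision for the sponsor; this review takes no position on it.

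2. In 5.5 and 11.7, keep the all-values rapid-rise count. Beside it, tabulate by arm a count that excludes Hb values from the start of ESA rescue or a transfusion until a prespecified interval afterwards, with that interval fixed before the data are examined.

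The cost is one reconciling sentence, carried into the synopsis, and one extra descriptive table row. Rescue is already reviewed at every visit from Day 1 (Appendix A), and medication dates are recorded (9.2.1); confirm that the CRF also captures transfusion dates. The small downside is that the second count uses fewer values, which is why it should accompany the all-values count and not replace it.

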#### 8.4.7 Late or Missed Doses

Subjects on vadadustat will be instructed to take the study drug at approximately the same time each day. If a dose is forgotten, subjects will be instructed to take the dose as soon as they remember during the same day.

- Daily dosing regimen: If a forgotten dose is not remembered on the same day, the subject will skip the dose and resume the normal dosing schedule the following day.
- TIW dosing regimen: If a forgotten dose is not remembered on the same day, the subject will take the dose on the following day (a non-dialysis day). If a forgotten dose is not remembered on the same day or the following day of a long interdialytic gap, the subject will take the dose on the subsequent day (the second non-dialysis day). Thereafter, the subject should resume the normal dosing schedule.
- Subjects will not double-up on missed doses.

Epoetin alfa dose (including handling of late or missed dose) will be administered at the site and titrated based on the subject's central laboratory Hb value and the approved epoetin alfa US PI for adult patients with CKD on dialysis.

#### 8.4.8 Iron Supplementation

IV iron will be administered based on ferritin and TSAT levels measured by the central laboratory according to the standardized, low-intensity, iron supplementation protocol in Table 1.

**TABLE 1 IRON SUPPLEMENTATION PROTOCOL**

	Ferritin <200 ng/mL	Ferritin 200-500 ng/mL	Ferritin >500 ng/mL
TSAT <20%	IV Iron 100 mg every treatment (max 400 mg/month)	IV Iron 50 mg weekly	Hold
TSAT 20-50%	IV Iron 100 mg every week	IV Iron 50 mg weekly	Hold
TSAT >50%	Hold	Hold	Hold

IV: intravenous; TSAT: transferrin saturation

Subjects already receiving oral iron supplementation as part of their treatment plan may continue their current treatment regimen. Because of the potential for oral iron to reduce the bioavailability of vadadustat, the study medication is not to be administered concurrently with an oral iron supplement (including multivitamins containing iron), iron containing phosphate binders, or any oral medications containing iron.

Subjects will be instructed to take any oral medications containing iron at least 2 hours after the dose of vadadustat.

#### **8.4.9 Rescue Therapy**

To ensure the safety of subjects and to standardize the use of rescue in the study, rescue therapy guidelines are provided.

##### **8.4.9.1 RBC Transfusion**

Investigators will use their local institution's transfusion guidelines when determining whether to transfuse a study subject. In general, in the event of an acute or severe loss of blood, a RBC transfusion will be administered as clinically indicated. In less severe instances but where there may be worsening of anemia or moderate to severe symptoms of anemia, RBC transfusions are permitted at the discretion of the investigator given medical necessity. Study drug (vadadustat or epoetin alfa) may be continued during the transfusion period.

Reasons for RBC transfusion will be captured in the appropriate CRF.

##### **8.4.9.2 ESA Use**

ESA administration will be allowed when medically necessary at the discretion of the investigator. In general, ESA will not be administered in subjects with Hb  $\geq 8.5$  g/dL, and ESA will be stopped when Hb  $\geq 9.0$  g/dL. ESA therapy will be administered using an approved ESA and dosing as per the local institution's guidelines and per the approved product label.

While receiving ESA therapy, subjects randomized to vadadustat must temporarily interrupt vadadustat. A minimum interval will be observed prior to restarting vadadustat after the last dose of ESA, and treatment will be resumed after the following intervals:

- 2 days after last dose of epoetin alfa
- 7 days after last dose of darbepoetin alfa
- 14 days after last dose of methoxy polyethylene glycol-epoetin beta

Following ESA administration, vadadustat will be resumed at the same dose as previously used or with one additional tablet (+150 mg) at the discretion of the investigator.

Reasons for ESA use will be captured in the appropriate CRF.

#### **8.4.10 Phlebotomy (Optional)**

If a subject's Hb exceeds 14.0 g/dL or the rate of rise of Hb raises concern to the investigator, the subject may be phlebotomized based on the investigator's clinical judgment. The method of phlebotomy will be in accordance with the study site's standard clinical practice.

#### **8.4.11 Treatment Compliance**

Throughout the study, subjects in the vadadustat arm will be guided regarding dosing compliance using an eDiary or paper dosing reminders. The focus of the vadadustat eDiary is to guide subjects to remind them of the dose, instruct them to hold their dose for the PK/PD sample dates and guide them if they have transitioned from daily dosing to TIW dosing. Subjects will also be questioned at study visits on whether they have questions or have experienced any problems related to the dosing of vadadustat. The investigator will also maintain drug accountability logs itemizing all study drugs dispensed to and returned from each subject during the study.

Treatment compliance will be determined from these logs, subject questioning, and the study drug Case Report Form (CRF).

For epoetin alfa, the dose that is administered is required to be entered in the electronic data capture (EDC) system, and the EDC system will be used to determine dosing compliance.

Subjects who miss doses will be counseled on the importance of compliance.

#### **8.4.12 Continuation of Treatment**

Subjects in the vadadustat dosing groups will not receive vadadustat beyond the Treatment Period of approximately 20 weeks. However, enrollment may be increased by up to approximately 20 additional subjects in the Main study and up to approximately 30 additional subjects in the ESA hyporesponder parallel study to ensure adequate data are captured for the primary, PK/PD, and safety endpoints. Subjects in the vadadustat dosing groups who complete Visit 14 (Week 20), or discontinue early, will resume dosing with epoetin alfa (or another ESA) as per standard of care after all EOT procedures are completed.

### **8.5 Prior and Concomitant Therapy**

#### **8.5.1 General**

Any medicinal product, prescribed or non-prescribed (including vitamins, minerals, natural and herbal remedies, topicals, inhaled, intranasal and dietary supplements) taken before entering the study is considered prior medication. All medicinal products other than the study drug, including prescribed or non-prescribed treatments used during the Treatment Period will be considered concomitant medication.

#### **8.5.2 ESAs**

Co-administration of any ESA with vadadustat is prohibited. In the setting of ESA rescue therapy, the initial dose of ESA rescue therapy may be administered on the same day as the last vadadustat dose prior to vadadustat dose interruption (see [Section 8.4.9.2, ESA Use](#)) if deemed medically necessary at the discretion of the investigator. Guidelines for ESA administration as rescue therapy are provided in Section 8.4.9.2, ESA Use. All efforts will be made to avoid inadvertent administration of ESAs resulting from adherence to ESA hemodialysis center protocols (e.g., DaVita ESA protocols for patients on hemodialysis). If ESA is inadvertently administered to subjects actively receiving vadadustat treatment, vadadustat treatment will be stopped and the event will be reported as a protocol deviation. A minimum interval will be observed prior to restarting vadadustat after the last dose of ESA. Vadadustat treatment may be resumed after the following intervals:

- 2 days after last dose of epoetin alfa
- 7 days after last dose of darbepoetin alfa
- 14 days after last dose of methoxy polyethylene glycol-epoetin beta

### **8.5.3 HMG-CoA Reductase Inhibitors (Statins)**

Exposures to atorvastatin and an active metabolite (para-hydroxy) were mildly increased in the setting of vadadustat co-administration in healthy adults. No dose adjustment of atorvastatin is recommended.

Exposures to simvastatin and an active metabolite (beta-hydroxy acid) were both mildly to moderately increased with co-administration of vadadustat in healthy adults. For subjects taking vadadustat who are concomitantly taking simvastatin, the recommended maximum daily dose of simvastatin is 20 mg. Investigators should review simvastatin dosing and consider clinical guidelines and local prescribing information including specific guidance in product labels with reference to renal impairment as well as hepatic impairment, concomitant medications and other medical factors relevant to the management of the subject.

Exposure to rosuvastatin was moderately increased with co-administration of vadadustat based on a study in healthy adults. For subjects taking vadadustat who are concomitantly taking rosuvastatin, the recommended maximum daily dose of rosuvastatin is 10 mg. Investigators should review rosuvastatin dosing and consider clinical guidelines and local prescribing information including specific guidance in product labels with reference to renal impairment as well as hepatic impairment, concomitant medications and other medical factors relevant to the management of the subject.

Exposure to pravastatin was studied in the setting of vadadustat co-administration in healthy adults. There was no interaction. No dose adjustment of pravastatin is recommended.

Exposures to the other statins may be increased with co-administration of vadadustat. When used with vadadustat, upward titration of other statins to higher doses should be done with caution.

